5.4.7 Presentation of Results

Model parameters and predictions will be presented in tables. In addition, data will be plotted as scatter plot with concentration on the abscissa and ΔQTc on the ordinate, for the concentrations of AQ, DEAQ, ATV, CG and PG. A regression line corrected for the time effect will be added together with a 90 % confidence band. In addition, a decile plot of the residuals by concentration will be given.

Additionally, goodness of fit plots will be produced.

5.4.8 Assay sensitivity

The anticipated effect of the meal at -1 h before drug administration will be used to show assay sensitivity [2]. This meal is expected to produce a shortening of $QTcF$ at the 1, 2 and 3 h timepoints after the meal by 5 – 10 ms. This shortening will be investigated by looking at the estimates of the time effect in the primary model at these timepoints. If the two-sided 90 % CI for all three of these estimates are completely below nought for both days, assay sensitivity will be deemed shown. If this is not the case, a Hochberg procedure will be applied testing the null hypothesis that at least one of the six contrasts is negative. More specifically, for Day 1, the estimates of the time effect will be used directly, while for Day 3, the difference of these timepoints to the estimate for the -35 min predose timepoint will be used.

The time course of the time effect will also be displayed graphically together with two-sided 90 % CI.

Note: The protocol mentioned that assay sensitivity would be evaluated using the estimates of the time effect representing the effects of breakfast and lunch of Days 1 and 3. The effect of breakfast on the two days only will be used, as the first timepoint after lunch is already at 8 h, i.e. 3 hours after the meal.

5.4.9 PK/J-Tpeak statistical modelling

Similarly to the analysis done for QTc and using the same primary linear model on adjudicated ECGs, an exploratory analysis of J-Tpeak using JTcJ ($J\text{-Tpeak}_c = J\text{-Tpeak}/RR$ power 0.58 with RR in seconds) will be performed to explore the drug related JTcJ interval changes relative to plasma PK concentrations.

5.5 Telemetry and Holter evaluations

Cardiac telemetry and Holter data will be listed.

5.6 Vital Signs

Vital signs data (systolic and diastolic blood pressure, pulse rate, respiratory rate, temperature) will be listed for individual subjects. Summary statistics of absolute (observed) values and changes from baseline will be calculated for each parameter and scheduled timepoint by treatment group.

Out-of-reference-range values will be flagged as high (H) or low (L) and as being clinically relevant or not: the number of subjects presenting out-of-range and clinically relevant values will be summarised.

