g: Vital signs and 12-lead ECG to be carried out prior to any blood sampling (where time points coincide). Vital signs will be measured after rest of at least 5 minutes in supine position and in standing at screening only. From Cohort 2 onwards, standing blood pressure measurement will be performed at 2H and 5H post-dose (on study days 1, 2 and 3). In addition to these time-points, an unscheduled standing blood pressure measurement should also be performed if a subject wish to leave the bed between these time-points.

h: Continuous 12-lead telemetry will be recorded from at least 1-hour pre-dose to 24 hours post-dose on Day 1 and Day 3.

i: At screening Holter will be performed to exclude pre-existing ECG abnormalities.

j: Coagulation at screening and Day -1.

k: pre-dose. Samples will be analysed only if required as per the Adaptive Feature number 9.

Table 2. Detail schedule of assessments for in-house stay

Study Day	Time (h)	PK blood sampling	Meals	12-lead ECG ^a	Vitals ^b	
D1	-3			X		
	-2.5			X		
	-2			X		
	-35 minutes	X			X	
	-30 minutes		X ^c			
	0					
	1	X			X	
	2	X			X ^e	
	3	X				
	4	X				
	5	X		X ^c	X	X ^e
	6	X			X	
D2	8	X		X	X	
	10		X			
	12	X		X		
	-35 minutes	X		X	X	
	-30 minutes		X ^c			
D3	0					
	2				X ^e	
	5				X ^e	
	-3			X		
	-2.5			X		
	-2			X		
	-35 minutes	X			X	
	-30 minutes		X ^c			
	0					
	1	X			X	
	2	X			X	X ^e
	D4	3	X		X	
4		X		X		
5		X		X	X ^e	
6		X		X		
8		X		X	X	
10			X			
12		X		X		
24		X	X ^d	X	X	

a: 12-lead ECG will be measured in triplicate after a rest period of at least 10 min.

b: Vital signs will be measured after rest of at least 5 min in supine position.

-
- c: Breakfast is the first meal and will be given at 30 minutes pre-dose. The 5-hour procedures are to be completed prior to lunch being given.
 - d: Optional breakfast after clinical assessments.
 - e: Standing blood pressure measurement will also be performed.

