- Any other ECG abnormalities in the standard 12-lead ECG and 24-hour 12 lead Holter ECG or an equivalent assessment which in the opinion of the Investigator will interfere with the ECG analysis.

Subjects with borderline abnormalities may be included if the deviations do not pose a safety risk, and if agreed between the appointed Cardiologist and the PI.

11. Has vital signs outside of the following normal range at screening or Day -1:
 - a. Blood pressure (BP):

Supine BP (after at least 5 minutes of supine rest):

 - Systolic blood pressure: 90 - 140 mmHg.
 - Systolic blood pressure drop of >20mmHg on standing (at the time-points specified in Table 1)
 - Diastolic blood pressure: 40 - 90 mmHg.
 - b. Pulse rate (after at least 5 minutes of supine rest):
 - Less than 40 or greater than 100 beats per minute
12. Positive test for Hepatitis B surface antigen (HBsAg), Hepatitis C antibody (HCV Ab), or human immunodeficiency virus antibody (HIV Ab) at screening;
13.
 - a. AST, ALT or bilirubin measurement above the laboratory reference ranges, at screening or Day -1.
 - b. Haemoglobin or platelet count outside of the laboratory reference ranges.
 - c. or any other clinically significant abnormal haematological measurement (per the Investigator's discretion).
14. Positive test results for alcohol or drugs of abuse at screening or Day -1.
15. Female subjects who are pregnant (including a positive serum pregnancy test at screening and on Day-1) or breastfeeding.
16. History or clinical evidence of substance and/or alcohol abuse within the 2 years before screening. Alcohol abuse is defined as regular weekly intake of more than 14 units (for both males and females), using the following NHS alcohol tracker <http://www.nhs.uk/Tools/Pages/drinks-tracker.aspx>.
17. Use of tobacco in any form (e.g., smoking or chewing) or other nicotine-containing products in any form (e.g., gum, patch, electronic cigarettes) within 3 months prior to the planned first day of dosing.
18. Has used any other prescription medication (excluding hormonal contraception, hormone replacement therapy) within 14 days or 10 half-lives (whichever is longer) prior to Day 1 of the dosing period that the Investigator judges is likely to interfere with the study or pose an additional risk in participating.

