The pharmacy staff preparing the investigational products will not be blinded to study drug assignment. During the study, the individual randomisation codes will be kept in the site's clinical trials pharmacy, accessible to the pharmacy personnel only. Upon completion of the study, after the database lock and after the blind is revealed, the randomisation list will be filed in the Trial Master File.

Sponsor staff involved in clinical decision-making (such as those involved in SRC decisions) will be blinded to study drug assignment.

Study numbers will not be reallocated once assigned.

4. General notes for statistical analyses

In general, descriptive statistics for continuous variables will include number of non-missing values (n), arithmetic mean, standard deviation (SD), median, minimum, and maximum.

Descriptive statistics for PK parameters will include number of observations, arithmetic mean (n), standard deviation (SD), arithmetic coefficient of variation (%CV), geometric mean, geometric %CV, median, minimum and maximum.

Categorical variables will be summarized using frequency counts and percentages.

For all tables, except PK parameter tables, descriptive statistics for minimum and maximum will be presented with the same decimal digits as the original data, and with 1 more decimal place than the original data for mean and median; SD will be reported with 2 more decimal places than the original data.

PK parameters will be presented as follows in the listing: C_{max} and T_{max} will be presented as given in the raw data; AUC_{0-t} , $AUC_{0-\infty}$, λ_z , $t_{1/2}$, CL or CL/F, and Vd or V_d/F will be presented with 3 decimal places. Descriptive statistics for PK parameters will be presented with decimal places as appropriate for the particular parameter and treatment group. SAS v9.3 or higher or Phoenix WinNonLin v7 or higher may be used for the determination of Pharmacokinetic parameters.

The analyses will be presented by treatment group. All collected data will be presented in by-subject listings. Listings will be ordered by treatment group and subject number and will include all randomized subjects.

Baseline will be defined as the last non-missing value among assessments recorded prior to first administration of study drug. Changes from baseline values will be calculated as the post-baseline assessment value minus the baseline value. Only observed values from scheduled time points will be used to create summary tables.

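### SAP 5.6 does not distinguish posture and plans no standing-minus-supine blood pressure difference, so the planned tables do not show how many subjects per arm had a postural fall

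*SAP*

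**What the plan says.** **Collection.** Protocol Table 1, footnote g, states: "From Cohort 2 onwards, standing blood pressure measurement will be performed at 2H and 5H post-dose (on study days 1, 2 and 3"). Table 2 marks the vital signs at those six time points with footnote e, "Standing blood pressure measurement will also be performed", while its footnote b makes the ordinary reading supine. The two readings are therefore taken at the same nominal time. For the rest of the schedule, footnote g says: "Vital signs will be measured after rest of at least 5 minutes in supine position and in standing at screening only". It also asks for an unscheduled standing reading if a subject wants to get up between the two time points.

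**Postural threshold.** The only one in either document is in exclusion criterion 11 (Protocol 5.4), applied at screening or Day -1: "Systolic blood pressure drop of >20mmHg on standing (at the time-points specified in Table 1").

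**Analysis.** SAP 5.6 begins: "Vital signs data (systolic and diastolic blood pressure, pulse rate, respiratory rate, temperature) will be listed for individual subjects". It continues: "Summary statistics of absolute (observed) values and changes from baseline will be calculated for each parameter and scheduled timepoint by treatment group". It then adds: "Out-of-reference-range values will be flagged as high (H) or low (L) and as being clinically relevant or not", with counts of subjects. Protocol 10.3 plans the same outputs. Neither section mentions standing readings.

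**Baseline.** SAP 4 (General notes) states: "Baseline will be defined as the last non-missing value among assessments recorded prior to first administration of study drug". It has no rule on posture. The same section limits summary tables to scheduled time points and sends all collected data to by-subject listings ordered by treatment group.

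**The concern.** Paired supine and standing readings are informative mainly through their within-subject difference, and that difference is the one quantity the SAP does not derive. The SAP also leaves open whether standing readings enter the blood pressure summaries at all, whether they form a parameter of their own, and what their baseline would be.

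At stake is a tolerability description by arm. The protocol lists dizziness as very common with amodiaquine (1.2.2.1) and as an event that both products share (1.2.2.3). The four arms are meant to separate the contribution of each treatment (1.1). A count of postural falls by arm serves that purpose and would not come out of the SAP as written.

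**Working it through.** Neither document gives a figure to reproduce. The check is whether any planned output yields the number of subjects per arm with a postural fall.

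**1. Change from baseline.** The last blood pressure before the first dose is the Day 1 reading at -35 minutes, which is supine. The only scheduled standing reading before dosing is at screening, which Table 1 places between Day -21 and Day -2. A standing change from baseline therefore has two possible references:
- the supine Day 1 value, in which case it contains the ordinary effect of standing up;
- the screening value, which can be about three weeks old.

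Neither is the same-time postural difference.

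**2. Out-of-range flags.** Neither SAP 5.3 nor SAP 5.6 states a blood pressure range. Assume 90 to 140 mmHg, the supine systolic eligibility range in exclusion criterion 11. A subject at 111 supine who falls by 21 reads 111 - 21 = 90 standing and is not flagged. The clinical-relevance label in SAP 5.6 is attached to out-of-range values, so it does not reach this subject either.

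**3. Separate tables by posture.** The SAP does not promise these. If they were made, and the same subjects contributed to both, subtracting the means would give the mean drop. It would not give the count. With a common SD σ for both postures and correlation ρ, the drop has SD σ√(2(1 - ρ)). Assume a supine mean of 118, a standing mean of 113 (mean drop 5) and σ = 10. Then P(drop > 20) = 1 - Φ(15 / SD of drop):

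| ρ | SD of drop | z | P(drop > 20) |
|---|---|---|---|
| 0.2 | 12.65 | 1.186 | 11.8% |
| 0.5 | 10.00 | 1.500 | 6.7% |
| 0.8 | 6.32 | 2.372 | 0.9% |

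The two posture tables would look identical in all three rows, yet the share of subjects with a drop above 20 mmHg varies about 13-fold. All these inputs are assumed. The point is only that by-posture means and SDs do not determine the count.

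**4. Listings and adverse events.** Every pair appears in the listings, by arm. Under Protocol 8.1 and 8.3, a fall that is symptomatic, needs intervention or is judged clinically significant by the investigator can be reported as an adverse event, and SAP 5.1 tabulates those by arm. An asymptomatic fall not judged significant appears in listings only. The unscheduled standing readings are likewise confined to listings.

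**5. How many subjects have pairs.**
- Dosed in total: 20 + 24 = 44, which agrees with 8 + 3 × 12 = 44 by arm.
- Assume Cohort 1 was the sentinel group of 12 in Protocol 3.3.4, with 4 on Treatment 1 and at least 2 on each other treatment.
- Subjects with scheduled pairs: at most 44 - 12 = 32, giving at most 32 × 2 × 3 = 192 pairs.
- Combination arm: 8 - 4 = 4. This is approximate, because the limit of three combination subjects per later cohort (Protocol 3.3.7) would give 4 + 3 = 7, not the 8 in SAP 3.1.
- Each other arm: at most 12 - 2 = 10.

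If the true proportion with a fall were 20% (assumed), the chance of seeing at least one case would be 1 - 0.8^4 = 0.59 with 4 subjects and 1 - 0.8^10 = 0.89 with 10.

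**The case against.** The strongest reply is that little is lost. The study is exploratory and descriptive and was not formally sized. Vital signs are supine by default (Protocol 7.5.1 and Table 2, footnote b), so SAP 5.6 can be read as a coherent supine analysis. Every pair is listed by arm, important falls can be reported as adverse events, and the combination arm has only about four subjects with pairs. All of this stands, and it limits the point to a descriptive addition. It does not supply the missing count, and the SAP does not say that its summaries are supine only.

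A reader might infer more than the documents support:

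- **That the data cannot show a postural drop by arm.** They can, because the listings hold every pair. It is the planned summaries that do not show it.
- **That posture confounds the treatment comparison.** A standing value set against a supine baseline would be hard to interpret within an arm, but the placebo arm has the same shift at the same time point.
- **That a protocol outcome was left out.** The 20 mmHg drop is an eligibility threshold only. No section makes it a post-dose outcome.
- **That the primary endpoint fails.** Its vital-signs component names systolic pressure, diastolic pressure and pulse rate, with no postural element. Nor does any section say that the standing readings were added for an analysis by arm. Their pairing with a check whenever a subject wants to leave bed reads at least as well as bedside monitoring.
- **That the share of missed falls is known.** With 90 to 140 mmHg borrowed as the range, and supine systolic pressure assumed normal, truncated to that range, with mean 115 to 120 and SD 10, 66% to 81% of subjects start at 111 or higher and could fall by 21 mmHg unflagged. That is the proportion with room to fall. It does not estimate falls that will be missed.

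**Conclusion.** The point holds as a gap in the planned outputs. SAP 5.6 leaves posture undefined and derives no standing-minus-supine difference, so the tables will not give the number of subjects per arm with a postural fall. Range flags and separate by-posture means cannot replace that count.

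The gap is modest. It affects a descriptive safety table with at most 32 contributing subjects, about 4 of them on the combination. Both figures rest on the assumption that Cohort 1 was the 12-subject sentinel group; Cohort 1 itself has no scheduled post-dose pairs. The normal-model and range-flag figures are illustrations on assumed inputs, since the documents state neither a blood pressure reference range nor any expected values. The change is worth making because the readings are already scheduled and the derivation is simple.

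**What to change.** In SAP 5.6:

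1. State that change from baseline in blood pressure uses supine readings only.
2. Derive standing minus supine systolic and diastolic pressure at screening and at each scheduled post-dose paired time point (2 h and 5 h on Days 1, 2 and 3). Summarise by treatment and time point.
3. Tabulate by treatment the number of subjects with any post-dose systolic drop above 20 mmHg, using subjects with at least one post-dose pair as the denominator and showing that denominator. Describe the cut-off as a descriptive one borrowed from exclusion criterion 11, not a protocol outcome criterion. Because that criterion excludes anyone with such a drop at screening, a post-dose case is new relative to entry.

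Add a table note that Cohort 1 has no scheduled post-dose pairs and that unscheduled standing readings are listed only.

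The cost is one derivation, applied to systolic and diastolic pressure, and one or two tables. No new measurement or change to study conduct is needed.

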5.7 Physical Examination

Physical examination data will be listed individually.

5.8 Profile of Mood Scale questionnaire

Data from the Profile of Mood Scale (POM) questionnaire will be used to calculate a general score called the Total Mood Disturbance score, as well as scores for the 7 items which are Tension, Anger, Fatigue, Depression, Esteem-related Affect, Vigour and Confusion. The scoring approach is presented in the Appendix 1.

Results from the POM questionnaire will be listed and along with changes from baseline will be summarised using descriptive statistics (n, mean, median, standard deviation, minimum, maximum) for the Total Mood Disturbance score followed by the score for each of the 7 items.

5.9 Basic Neurological Examination

Basic Neurological Examination data will be listed only.

6. Pharmacokinetic Analysis

All plasma concentration data will be listed for each individual subject and summarized at each time point by treatment group. Individual and mean concentrations versus nominal time on linear and semi-log scales will be presented graphically. The PK set will be used to present the summary of PK parameters.

6.1 Values Below the Limit of Quantification and Missing Values

If a Below the Level of Quantification (BLQ) value occurs in a profile before the first measurable concentration, it will be assigned a value of zero concentration. If a BLQ value occurs after a measurable concentration in a profile and is followed by a value above the lower level of quantification, then the BLQ value will be omitted following visual inspection of the plasma concentration versus time profile to assess the appropriateness of this assignment. If a BLQ value occurs at the end of a collection profile (after the last quantifiable concentration), the value will be treated as missing data. If 2 BLQ values occur in succession, the profile will be deemed to have terminated at the first BLQ value and any subsequent concentrations will be omitted from PK calculations following visual inspection of the plasma concentration versus time profile to assess the appropriateness of this assignment.

Samples with no reportable value due to a bioanalytical issue or missing samples will be set to missing, and will not be included in the PK calculations.

When calculating the mean or median value for a concentration at a given time point, all BLQ values will be set to zero except when an individual BLQ falls between 2 quantifiable values, in which case it will be omitted.

For tabulation, graphical representation, and calculation purposes, all samples with no reportable value (or missing samples) observed after dosing will be set to missing.

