The remaining three treatments will be re-randomised in such a way that across the whole study there will be still 12 subjects dosed with Treatment 2, 12 subjects with Treatment 3 and 12 Subjects with treatment 4. This is taking into account both the already dosed subjects with their originally randomised treatments and the newly randomised subjects yet to be included. Furthermore, within each cohort of up to eight subjects, each of the three treatments (2, 3, and 4) needs to be represented with a maximum of four and a minimum of one subject in the same cohort.

Subjects will be screened within 20 days prior to entering the study on Day -1. Each subject will receive verbal and written information followed by signing of the Informed Consent Form (ICF) prior to any screening procedures taking place. Subjects will be admitted to the study unit on Day -1 and will be discharged on Day 4.

All subjects will attend the unit for an outpatient visit on Days 8, 15, 22, 29 and a follow-up visit on Day 36 (+/- 1 day). All the assessments performed during the study are detailed in the study schedule of assessments (Table 1 and Table 2). Study design features as well as number of subjects may be adapted according to the Adaptive Features (Table 3). This study will use a sentinel dosing strategy, for full details see Section [3.3.4](#).

Number of subjects:

The planned total number of subjects for this study will be 52.

Main criteria for admission:

Black males or females, of sub-Saharan African origin (both parents are black and are of sub-Saharan African origin) will be included if they are aged between 18 and 45 years with a body mass index (BMI) between 18.0-25.0 kg/m². Subjects must agree to use effective methods of contraception.

Main exclusion criteria are: Current or recurrent disease (or condition) that could affect the action, absorption or disposition of ATV-PG or AQ, and any other significant disease or disorder which, in the opinion of the Investigator, may either put the subject at risk because of participation in the study, may influence the result of the study, or the subject's ability to participate in the study.

Anticipated test treatment(s) and mode of administration:

Oral doses of ATV-PG (1000-400 mg) and AQ (612 mg) administered once daily on Days 1 to 3 in the fed state (see Section [6.1.2](#) for details).

Reference treatment(s) and mode of administration:

Oral doses of unmatched placebo for ATV-PG and AQ.

Criteria for evaluation:

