Procedure	Scr D-21-D-2	D -1	D1	D2	D3	D4	D8	D15	D22	D29	Follow-up visit D36+/-1
Informed consent	X										
Demographic data	X										
Medical history and current medications	X	X ^a									
Urine drugs of abuse screen	X	X									
Breath alcohol test	X	X									
Serology HIV1&2, Hep B&C	X										
Serum pregnancy test ^b	X	X								X	X
FSH ^c	X										
Inclusion/Exclusion criteria	X	X									
Smoking history (pack/year) and current	X										
Study Residency		X	X	X	X						
Check-in		X									
Check-out						X					
Non-residential visit							X	X	X	X	X
Randomisation			X								
Study drug administration ^d			X	X	X						
Meals ^e		X	X	X	X	X					
Safety and tolerability:											
AE recording/ concomitant medication	X	X	X	X	X	X	X	X	X	X	X
Physical examination	X	X ^f			X ^f	X					
Vital signs ^g	X		X	X	X	X					X
Telemetry ^h				X		X					
24h Holter ECG ⁱ	X										
12-lead ECG in triplicate ^g	X		X	X	X	X	X	X	X		X
Body height	X										
Body weight	X										
BMI	X										
Haematology/Biochemistry/Coagulation ^l	X	X		X	X	X	X	X	X	X	X
Urinalysis	X	X								X	
Basic neurological exam			X	X	X	X	X			X	
Questionnaire Profile of Mood Scale (POM)			X			X	X			X	

Procedure	Scr D-21-D- 2	D -1	D1	D2	D3	D4	D8	D15	D22	D29	Follow- up visit D36+/-1
CYP2C8 Genotyping Sample			X ^k								
Pharmacokinetic assessments											
PK blood sampling - ATV			X	X	X	X	X	X			
PK blood sampling - PG/CG			X	X	X	X					
PK blood sampling - AQ			X	X	X	X					
PK blood sampling - DEAQ			X	X	X	X	X	X	X		

a: Update only.

b: Females of childbearing potential only.

c: A hormonal test for FSH will be done for females at screening who believe they are post-menopausal. If female subjects are confirmed as post-menopausal then these subjects will not require any further serum pregnancy tests.

d: Dosing will be carried out in the fed state. On the morning of each dosing day (Days 1, 2 and 3), a standardised meal will be served 30 mins before dosing and must be finished 10 mins before dosing, firstly with the ATV-PG / placebo tablets, followed by the AQ dispersible/ placebo tablets.

e: Standard meals will be served at standard unit times. On Days 1 to 3, the 1st meal is breakfast, lunch given 5 hours post-dose and no other meals are given before completion of the 2-4 hours post-breakfast cardiac assessments. On Day 4 (dismissal day) meals will be optional.

f: Symptom directed examination.

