10.5.2 Statistical Analysis on PK Parameters

Plasma concentrations will be listed and summarised by time point (N - the number of subjects, n - the number of samples, n(LLOQ) - the number of samples <LLOQ, arithmetic mean, SD - standard deviation, CV - coefficient of variation, geometric mean, median, minimum, maximum). The PK parameters will be listed for each subject and summarized for each treatment group using descriptive statistics (N - the number of subjects, arithmetic mean, SD - standard deviation, CV - coefficient of variation, geometric mean, median, minimum, maximum).

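### The BLQ exception for mean and median concentrations in SAP 6.1 is not limited to one dosing interval, so AQ, PG and CG troughs on Days 2 and 3 are handled differently from the Day 4 trough

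*SAP*

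**What the plan says.** SAP 6.1 has several BLQ rules for profiles and PK calculations. It then gives summary statistics by sampling time a separate rule, namely that "all BLQ values will be set to zero except when an individual BLQ falls between 2 quantifiable values". A value that meets this exception is left out. The SAP does not say whether the two quantifiable values must belong to the same dosing interval, and it does not define a profile per dose.

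The resulting summaries appear in tables by treatment group and in plots. SAP section 6 states: "Individual and mean concentrations versus nominal time on linear and semi-log scales will be presented graphically". Protocol 10.5.2 adds the number of samples below LLOQ at each time point: "n(LLOQ) - the number of samples <LLOQ, arithmetic mean".

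The dosing and sampling around the rule are as follows.

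- Study drug is "administered once daily on Days 1 to 3 in the fed state" (Protocol synopsis).
- Protocol Table 2 ("Detail schedule of assessments for in-house stay") takes PK samples on Day 1 at -35 min, 1 to 6, 8 and 12 h; on Day 2 at -35 min only; on Day 3 at -35 min, 1 to 6, 8 and 12 h; and on Day 4 at 24 h.
- In Protocol Table 1 the row "PK blood sampling - AQ" ends on Day 4, as does the PG/CG row. ATV sampling runs to Day 15, and the row "PK blood sampling - DEAQ" runs to Day 22.

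**The concern.** In a single-dose curve, a BLQ value between two quantifiable ones is an anomaly, and leaving it out is sensible. Here a BLQ trough before the Day 2 or Day 3 dose may simply be a low value at the end of a dosing interval. It lies between quantifiable samples because the next dose raises the concentration again. The same low value about 24 h after the Day 3 dose has nothing after it for AQ, PG and CG, so it can never meet the exception and enters as zero. The day of sampling, not the measurement, decides how it is treated.

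Dropping low values on Days 2 and 3 and counting them as zero on Day 4 pushes the first two summaries up relative to the third. A reader who uses the mean troughs or the mean concentration plots to judge accumulation over the three doses would see too little of it.

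**Working it through.** **Inputs.** Half-lives are from Protocol section 1: AQ 7.9 h, PG 8.03 h, CG 10.2 h, ATV 87.2 h, DEAQ 211 h. The LLOQ is not given (Protocol 7.10.1 refers to a separate bioanalytical report), and neither are trough levels. These are assumptions, shown as ranges. The plan states no figure of its own to reproduce.

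**Step 1: how the rule treats each trough (AQ, PG, CG).**

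| Sample | Neighbouring PK samples | BLQ value becomes |
|---|---|---|
| Day 2, -35 min | Day 1 12 h; Day 3 -35 min | omitted if isolated |
| Day 3, -35 min | Day 2 -35 min; Day 3 1 h | omitted if isolated |
| Day 4, 24 h | Day 3 12 h; none after | zero, always |

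The Day 2 and Day 3 troughs are adjacent samples. If both are BLQ, the wording allows two readings. On the narrower one, neither is an individual BLQ, so both become zero. On the broader one, any BLQ with quantifiable values somewhere before and after it is omitted.

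**Step 2: what the troughs should do.** The fraction left after 24 h is f = 2^(-24/t½). By superposition the troughs on Days 2, 3 and 4 are in the ratio 1 : 1+f : 1+f+f².

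- AQ: f = 0.122, giving 1, 1.12, 1.14
- PG: f = 0.126, giving 1, 1.13, 1.14
- CG: f = 0.196, giving 1, 1.20, 1.23
- ATV: f = 0.826; DEAQ: f = 0.924. BLQ troughs are implausible, and Day 4 is not their last sample.

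This treats the pre-dose samples as 24 h values. They are drawn 35 min (0.583 h) earlier, which for AQ is a factor of 2^(-0.583/7.9) = 0.95. The true AQ Day 4/Day 2 ratio would then be nearer 1.137 × 0.95 = 1.08. The unequal BLQ handling comes on top of that.

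**Step 3: a small case.** Treatment 1 has 8 subjects (SAP 3.1). Suppose one is quantifiable on Day 2 but BLQ on Days 3 and 4, and the other seven have mean m on both later days. The Day 3 mean is 7m/7 = m. The Day 4 mean is (7m + 0)/8 = 0.875m. That is a 12.5% drop produced by the rule alone, on either reading.

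The median moves too. With 12 subjects it lies between ranks 6 and 7. If the two lowest are omitted it lies between ranks 7 and 8.

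**Step 4: simulation, narrower reading.** Troughs are log-normal, with median 1 to 2 × LLOQ on Day 2, CV 50% or 80%, and within-subject correlation 0.3 or 0.8 (16 settings). End points are good to about 0.01.

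| Day 4/Day 2 ratio of means | True | SAP 6.1 as written | BLQ = 0 at every trough |
|---|---|---|---|
| AQ/PG | 1.14 | 0.94-1.10 | 1.15-1.30 |
| CG | 1.23 | 1.01-1.19 | 1.25-1.48 |

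For AQ/PG the ratio falls below 1 in 5 of the 16 settings, all at correlation 0.3. For CG it never does.

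**Step 5: the two readings compared, Day 4 against Day 3.** With median 0.8 to 2 × LLOQ, between-subject CV 50%, within-subject CV 20% or 40% and AQ-like accumulation, the true change is +1% to +2%. The narrower reading reports 0% to -9%, the broader one -4% to -57%.

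**The case against.** The strongest reply is that no planned result rests on these means. The PK endpoints are Cmax, tmax, AUC, λz and half-life, which follow other BLQ rules. No trough or steady-state comparison is planned. The concentration-QTc data set codes BLQ as zero (SAP 4.2). The hysteresis check in SAP 5.4.6 plots mean concentrations but looks at the timing of the maximum, which troughs do not determine. Individual concentrations are listed and plotted, and the BLQ count is tabulated. All of this stands and limits the point to descriptive output. The count reveals the BLQ values but does not correct the mean.

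It can also be said that, if a profile means one dosing interval, every BLQ trough becomes zero and the problem vanishes. That is a reasonable intention, but the SAP does not state it, and the sentence on means does not use the term.

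Three stronger readings are tempting and should not be adopted.

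- A reader might infer that the rule manufactures a fall of 3% to 20% from Day 2 to Day 4. That range (ratio 0.80 to 0.97) needs identical true troughs on all days. The half-lives in the protocol imply rising troughs, so the usual result is an understated rise.
- A reader might infer that every BLQ trough on Day 2 or 3 is dropped. On the narrower reading, only isolated ones are.
- A reader might infer bias between arms. All arms share the rule at each time point. It would act unequally only if co-administration changed the share of BLQ troughs, and Protocol section 1 rates the interaction potential as low.

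Finally, setting every BLQ trough to zero is not unbiased: it overstates the rise in the mean, as Step 4 shows. This too stands, and it shapes the fix.

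**Conclusion.** The point holds as a flaw in a stated rule, of minor consequence. For AQ, PG and CG, SAP 6.1 as written omits an isolated BLQ trough on Day 2 or 3 and counts a BLQ Day 4 trough as zero, so the three trough summaries are not comparable.

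On the narrower reading, with troughs assumed at 1 to 2 × LLOQ, accumulation is understated: 0.94 to 1.10 against about 1.14 for AQ/PG, and 1.01 to 1.19 against 1.23 for CG. In some AQ/PG settings the rise disappears or becomes a fall of up to about 6%. The broader reading gives a larger distortion.

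The size rests on an assumed LLOQ, assumed variability, superposition from terminal half-lives, and pre-dose samples treated as 24 h values. If no trough is BLQ, there is no effect. ATV, DEAQ, the PK parameters and the concentration-QTc data set are unaffected.

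**What to change.** Replace the exception in SAP 6.1 with wording such as: *For means and medians by time point, a BLQ value is omitted only if it lies between two quantifiable values from the same dosing interval. Pre-dose samples on Days 2 and 3 that are BLQ are set to zero, as is a BLQ 24 h sample on Day 4.* This keeps the exception for isolated anomalies within a curve, treats like samples alike, and agrees with the zero coding in SAP 4.2.

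Show the number below LLOQ at each time point, as Protocol 10.5.2 already plans, and state that the median is the summary to read where BLQ values are present. With all BLQ values kept as zeros, the median is unaffected as long as fewer than half are BLQ (at most 5 of 12, or 3 of 8). Means that include zeros are biased low and can overstate accumulation, so a footnote should say so.

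The cost is one or two sentences of SAP text and a table footnote. No data collection, sample size or endpoint changes. Where BLQ troughs occur, the Day 2 and Day 3 summaries will be lower than under the present wording.
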